**Please select which week you stopped experiencing the symptoms described below.**

**If you never experienced this symptom, please select N/A**

	During the first two weeks since my covid-19 diagnosis	During the third week since my covid-19 diagnosis	During the fourth week since my covid-19 diagnosis	I still experience this symptom	N/A - I never experienced this symptom
Shortness of breath					
Cough					
Fatigue					
Lack of taste					
Lack of smell					
Other					

If you answered "Other," please specify/describe additional symptom #1: \_\_\_\_\_

If you answered "Other," please specify/describe additional symptom #2: \_\_\_\_\_

If you answered "Other," please specify/describe additional symptom #3: \_\_\_\_\_

Comment - Optional (please add here anything else you might want to share with us regarding any symptoms and/or your quality of life since your covid-19 diagnosis) \_\_\_\_\_

Please write-in your blood pressure, taken anytime in the last 2 weeks: \_\_\_\_\_

Source of blood pressure (BP) equipment and method:

- BP was taken by machine at home
- BP was taken by machine at a pharmacy
- BP was taken manually in medical office

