## 1.0 Study Summary

Study Title	HMH Omega-3 Covid Recovery Study
Study Design	We will conduct a two-arm, double blind randomized 12-week study to supplement omega-3 (EPA + DHA) among 100 adults (age 18+) who had covid-19 and are experiencing possible after-effects from the illness (post-acute sequelae of covid-19, also called post-covid syndrome or long covid syndrome).
Primary Objective	The primary objective is to serve as a feasibility study for omega-3 fatty acid supplementation v. placebo in adult patients to limit long covid syndrome. This will serve as a proof-of-concept for a larger follow-up study to subsequently be conducted.
Secondary Objective(s)	Determine which of the post-covid symptom(s) are most impacted by omega-3 supplement.
Research Intervention(s)/Investigational Agent(s)	Participants will be assigned to one of two study arms and asked to take an Omega-3 supplement or placebo for 12 weeks. Participants will report symptoms bi-weekly throughout the study period. A spot blood sample to assess omega-3 levels will be done at baseline and at the end of the 12-week study period.  A survey will be used bi-weekly to assess health status and outcomes via patient self-report. Data on demographics and comorbidities such as obesity and diabetes will be collected at baseline. At the end of study participation, subjects will take a follow-up survey assessing feasibility.
IND/IDE #	IND # 157250
Study Population	Hackensack Meridian Health team members age 18+ who tested positive for COVID-19 28+ days prior and who are not already taking an Omega-3 supplement.
Sample Size	50 participants in each arm = 100 total for final analysis (up to 60 participants in each arm will be recruited if needed, dependent on attrition for a total of up to 120)
Study Duration for individual participants	Individual participants will be in the study for 12 weeks. During the 12 week study period, subjects will be sent a survey every two weeks. At the end of the 12 weeks, subjects will complete a short survey collecting feasibility and acceptability data.
Study Specific Abbreviations/Definitions	
 
• Hackensack Meridian Health (HMH)
 
• Center for Healthy Senior Living (CHSL)
 

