#### **4.2 Secondary and Exploratory Outcome Variables**

A separate analysis will be conducted to determine which post-covid symptom(s) are more impacted by omega-3 supplement. The Bi-weekly Symptoms and Quality of Life Post Covid-19 Survey (Appendix C) includes the four symptoms being measured (respiratory, fatigue, lack of taste, lack of smell). Therefore, this bi-weekly survey will be used for this efficacy analysis.

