## **17.0 Data Management and Confidentiality**

### **17.1 Data analysis plan**

All study data will be summarized with descriptive statistics. Continuous variables will be summarized with means, standard deviations, medians and ranges. Categorical variables will be summarized with counts and percentages. Data will be summarized overall and separately by the two study arms: Omega-3 supplement or placebo. In general, continuous endpoints will be compared between groups using t-tests or Wilcoxon rank sum tests, as appropriate. Categorical endpoints will be compared between groups using chi-square tests or Fisher's exact tests, as appropriate.

The primary analysis will be the comparison of groups on the long covid-19 symptoms recovery using a chi-square test or Fisher's exact test, as appropriate.

Additional exploratory analyses may be conducted to better understand relationships within the data.

Results with a p-value less than or equal to 0.05 will be considered statistically significant. No adjustments for multiple comparisons will be implemented as this is a feasibility study not statistically powered for analyses.

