## Bi-weekly Symptoms & Quality of Life Post Covid19 Survey

Thank you for agreeing to participate.

Please complete the survey below.

Please feel free to skip any question that makes you feel uncomfortable or just close the survey window if you change your mind and you no longer want to participate to our study.

Thank you for your time.

How was your overall health before you got sick with COVID-19?

- Excellent
- Very good
- Good
- Fair
- Poor

With whom do you live?

- Alone
- With family
- Roommates
- Other
- I do not want to answer this question

Please specify

**Considering the past 14 days, please rate your answers. Should you choose to not answer a question, please leave it blank.**

	Excellent	Very good	Good	Fair	Poor
In general, would you say your health is:					
In general, would you say your quality of life is:					
In general, how would you rate your physical health?					
In general, how would you rate your mental health, including your mood and your ability to think?					
In general, how would you rate your satisfaction with your social activities and relationships?					

Confidential

Page 2

In general, please rate how well you carry out your usual social activities and roles. (This includes activities at home, at work and in your community, and responsibilities as a parent, child, spouse, employee, friend, etc.)

To what extent are you able to carry out your everyday physical activities such as walking, climbing stairs, carrying groceries, or moving a chair?

Completely  
 Mostly  
 Moderately  
 A little  
 Not at all

How often have you been bothered by emotional problems such as feeling anxious, depressed or irritable?

Always  
 Often  
 Sometimes  
 Rarely  
 Never

How would you rate your fatigue on average?

Very Severe  
 Severe  
 Moderate  
 Mild  
 None

**Considering the past 14 days, please rate the amount of difficulty you had when doing the following activities. Should you choose not to answer a question, please leave it blank.**

	No difficulty	A little difficulty	Some difficulty	Much difficulty	I did not do this in the past 7 days
Dressing yourself without help					
Walking 50 steps/paces on flat ground at a normal speed without stopping					
Walking up 20 stairs (2 flights) without stopping					
Preparing meals					

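### The Appendix C symptom grid has no true answer for a symptom present at entry that resolves on study, and four of its five named symptoms have no other structured status item

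*Combined protocol and SAP*

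**What the plan says.** Section 4.2 lists four symptom domains (respiratory, fatigue, taste, smell) and states of Appendix C: "Therefore, this bi-weekly survey will be used for this efficacy analysis". Section 17.1 states: "The primary analysis will be the comparison of groups on the long covid-19 symptoms recovery", using a chi-square or Fisher's exact test. It does not define recovery.

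The Appendix C grid has five named symptom rows (shortness of breath, cough, fatigue, taste, smell) plus an *Other* row. Its instruction is "Please select which week you stopped experiencing the symptoms described below". Each row offers five answers: stopped in the first two weeks, in the third week, or "During the fourth week since my covid-19 diagnosis"; "I still experience this symptom"; or not applicable because never experienced.

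Elsewhere in the survey, fatigue has a past-14-day severity question, "How would you rate your fatigue on average", whose answers run from *Very Severe* to *None*. The introduction to the survey says "Please feel free to skip any question that makes you feel uncomfortable", and later instructions tell subjects to leave such items blank.

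On entry, section 1.0 describes people who "tested positive for COVID-19 28+ days prior". The inclusion list in section 10.0 requires an ongoing symptom that has lasted beyond 12 weeks from infection, and the exclusion list repeats that 12-week line as a reason to exclude. These three statements must be reconciled.

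**The concern.** The grid's stop times cover only the first four weeks after diagnosis, while the subjects who answer it are beyond that point and still symptomatic. The event the analysis needs is a symptom that was present at entry and has since gone, and no answer describes it. If that event is miscoded, or cannot be told apart from a skipped question, the recovery comparison in section 17.1 loses signal. The secondary question of which symptom is most affected could also turn on how each symptom is asked. Current status that is not recorded at each survey cannot be reliably reconstructed later.

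**Working it through.** **1. Time windows.** The plan gives no figure to reproduce. Inputs: the last stop option is week 4 after diagnosis (Appendix C); follow-up is 12 weeks (section 9.0); the entry wordings are those of sections 1.0 and 10.0. For the 12-week wording, diagnosis is assumed to be close to infection.

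- Grid ends: 4 × 7 = day 28.
- Follow-up: 12 × 7 = 84 days.
- 28+ day wording: earliest entry day 28; 28 + 84 = day 112. Study weeks are 5 to 16 at the earliest, starting where the grid ends. Overlap with weeks 1 to 4: none.
- More-than-12-week wording: earliest entry day 84; 84 + 84 = day 168. Study weeks are 13 to 24 at the earliest. Gap from the grid: 84 − 28 = 56 days, or 8 weeks.
- Exclusion-list line read literally with section 1.0: entry still falls on or after day 28.

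For a recovery on study, the three stop weeks are therefore too early, *still* is false and *never* is false. A stop week could be true under the 12-week wording only if diagnosis came more than 56 days after infection, or if a reinfection (permitted by section 6.2) led the subject to count from a new diagnosis.

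The same gap catches a second group. Entry needs only one ongoing symptom, so a subject enrolled for fatigue whose cough ended after week 4 but before entry has no true answer on the cough row from the first survey onward.

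**2. Other sources of symptom status.**

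- Appendix A records symptoms at screening only and combines shortness of breath with cough.
- Appendices B and D have no symptom-status item.
- The activity questions in Appendix C measure function.
- The Appendix C comment box is optional free text. The weekly call notes (section 17.3) are unstructured.
- The 6-month call (section 19.3) falls after week 12 and its content is not specified.

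Only fatigue has a structured alternative. Rows without one: 5 − 1 = 4 of 5. Section 4.2 domains without one: 4 − 1 = 3 of 4. These count rows on the form, not shares of the data.

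**3. Illustration of loss (all rates assumed).** Let p be true recovery and f the share of recoveries not recorded as such, equal in both arms, with no false recoveries.

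- Coded as not recovered: observed rate = p(1 − f).
- Left blank and dropped: observed rate = p(1 − f)/(1 − pf).

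At f = 0.50 with p = 20% v 40%, the second formula gives 0.10/0.90 = 11.1% v 0.20/0.80 = 25.0%.

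| f | Coded not recovered | Difference | Blank, dropped | Difference |
|---|---|---|---|---|
| 0.25 | 15% v 30% | 15 points | 15.8% v 33.3% | 17.5 points |
| 0.50 | 10% v 20% | 10 points | 11.1% v 25.0% | 13.9 points |
| 0.75 | 5% v 10% | 5 points | 5.9% v 14.3% | 8.4 points |

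With 50 per arm and a two-sided 0.05 test (section 17.1 does not state sidedness), power in the coded-not-recovered case falls from 59.0% at f = 0 to 43.4%, 28.6% and 15.5%. This takes all 50 per arm as having the symptom; a single-symptom comparison would have fewer.

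The shrinkage depends on the scale. In the coded-not-recovered case at f = 0.50, the risk ratio is unchanged: 20/10 = 40/20 = 2.0. In the blank-and-dropped case, the odds ratio is unchanged: (0.25/0.75)/(0.111/0.889) = (0.40/0.60)/(0.20/0.80) = 2.67.

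**The case against.** The best defence is that this is a feasibility study. Feasibility is the primary objective, section 4.1 bases that endpoint on Appendix D, and section 4.2 treats symptoms as secondary and exploratory. Section 17.1 says the study is not powered. An analyst could count any move from *still* to a stop week as recovery, and subjects can use the comment box or ask during the weekly call.

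Much of this stands. The Appendix D endpoint is unaffected. A move from *still* to a false stop week keeps some binary signal, and the documents do not show how often each answer would be chosen. But no such recoding rule is written. It would rest on untrue answers, and it would not recover blanks or recoveries marked *still*. Under section 8.0, completers are told their arm within 4 weeks of finishing, so a rule written late could be chosen with assignments known. Section 17.1 also calls the recovery comparison the primary analysis. That conflict with section 4.1 is a separate matter, and this point does not depend on it.

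A reader might infer more than the documents support:

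- **That every on-study recovery will be recorded wrongly, or that the symptom data are worthless.** Some signal survives, and the loss is unknown.
- **That fatigue is bound to look most affected.** Fatigue is also a grid row, and the plan does not say which item defines its recovery. The imbalance arises only if fatigue is scored from its rating and the others from the grid.
- **That the form favours one arm.** Subjects answer under blinding, so lost signal is more likely than a false difference.
- **That every effect measure shrinks.** The ratio results above show otherwise.

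**Conclusion.** The defect is real and needs fixing, because Appendix C is the only instrument named for the symptom efficacy analysis. As written, a symptom present at entry that resolves on study cannot be reported truthfully in the grid under either entry wording, edge cases aside. Nor can one that ended between week 4 and entry. For shortness of breath, cough, taste and smell, nothing structured makes up for this. Recoveries in these symptoms may appear as a false stop week, as *still*, as never experienced, or as a blank that looks like a permitted skip.

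The likely consequence is a smaller observed risk difference and lower power. If fatigue is scored from its rating, the comparison across symptoms is also uneven. How much is lost cannot be stated from the documents; the figures above rest on assumed recovery rates and on equal loss in both arms.

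**What to change.** **Form.** For each of the five named symptoms, add a current-status question for the past 14 days, with cough and shortness of breath asked separately. The *None* to *Very Severe* scale already used for fatigue is preferable because it also shows partial improvement. The minimum is one more grid option meaning stopped after the fourth week, or no longer present. Obtain one completed Appendix C survey after consent and before the first dose.

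**Section 17.1.** State that:

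- recovery is assessed only for symptoms present on the pre-dose survey: rated *Mild* or worse or, if only the grid is kept, answered as still experienced;
- recovery means *None* at week 12 or, if only the grid is kept, the new no-longer-present option;
- a blank is missing, and counts as neither recovered nor unrecovered;
- one named item defines fatigue recovery;
- each symptom is reported separately, and the definition of overall recovery is fixed before any results by arm are seen.

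How symptoms combine into overall recovery is for the team to choose, provided it is written down in time. Separately, reconcile the entry wordings in section 1.0 and in both lists of section 10.0.

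**Cost.** One REDCap edit, a few sentences in section 17.1, an IRB amendment, a slightly longer survey and possibly one extra survey send. The grid-only option is shorter but gives no measure of partial improvement.

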## Appendix D: Follow-up Feasibility Survey & Study Discontinuation Verification

Confidential

Page 1

## Follow-up Survey - Covid Recovery Study

Please complete the survey below.

Thank you!

Were the instructions on how to take the pills clear?

Yes  
 No  
 Neutral / I don't know

If no, why not?

Did you not take the pills (skip one or more doses) at any time during 12-week study? (please refer to your pill log calendar)

No  
 Yes

If yes, how often did you not take the pills?

For how many days in a typical week did you take the pills?

Please include any comments about missed doses here:

Were the pills easy to take?

Yes  
 No  
 Neutral / I don't know

If no, why not?

Did taking the pills interfere with your daily activities somehow?

Yes  
 No  
 Neutral / I don't know

If yes, how?

How satisfied were you with your experience taking the pills?

Very satisfied  
 Satisfied  
 Neutral  
 Dissatisfied  
 Very dissatisfied

Are you willing to be contacted in the future about opportunities to participate in other research studies?

Yes  
 No

Confidential

Page 2

Since starting your participation in this study, has any doctor or other health care provider told you that you have any of the following illnesses? (please check all that apply)

- Diabetes or high blood sugar
- Hypertension or high blood pressure
- High cholesterol
- Stroke (ischemic or hemorrhage)
- Chronic lung disease such as asthma, emphysema, or chronic bronchitis
- Heart disease
- Cancer (other than skin cancer)
- Depression
- HIV/AIDS
- Other

If you answered "Other," please specify:

---

Please share anything else you would like us to know about your experience participating in this study:

---

During the 12-week study, did you receive the covid-19 vaccine?

Yes  
 No

If you did receive the covid-19 vaccine, did you experience any side effect(s)?

---

For how long did you experience side effect(s)? (please specify in # of days)

---

Is there anything else you would like to tell us that you might be important that we did not ask about?

---

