## **4.0 Study Endpoints**

### **4.1 Primary Outcome Variables**

The primary endpoint is evaluation of feasibility and acceptability of omega-3

supplementation v. placebo to limit post-covid syndrome among adult patients. The Follow-up Feasibility Survey (Appendix D) will be used for this analysis.

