#### **6.2 Research Procedures**

For an overview of the study, please see figure 1 below.

1. Team members who email the study team at the address on the flyer will be sent an eligibility survey in REDCap to determine if study inclusion criteria are met.
2. Those who meet study inclusion criteria will then be sent the study consent form in REDCap, and encouraged to call or email the study team with questions.

3. If the patient expresses further interest in study participation, s/he will be consented via REDCap and then will be sent a link to the baseline survey in REDCap.
4. Upon consent, RC will assign ID# and enter the subject into REDCap (study data management system).
5. Subjects will be randomly assigned to receive 3 Omega-3 (EPA+DHA) mini-capsules twice daily (total of 2,100mg per day) for 12 weeks in the experimental intervention arm or three placebo mini-capsules twice daily for 12 weeks.
  - Study supplement or placebo are supplied at no cost to the subject and will be mailed to the subject's home.
  - Study subjects will receive two shipments over the course of study participation.
    - Package 1 upon enrollment
    - Package 2 at the end of week 4
  - Subjects will also receive, in these shipments, two spot blood sample tests for omega-3 levels, and directions indicating when to use the test kits.
6. All study subjects in each arm will be asked to give a spot sample (2 drops) of blood at baseline and again after 12 weeks (end of study participation). This will be done using OmegaQuant test kits that are mailed to the subject's home. The de-identified samples will be mailed by the subject in the provided envelope to OmegaQuant Lab, associated with University of South Dakota Medical Center, for analysis of omega-3 levels. These tests involve no cost to the subject. Subjects will be informed of their omega-3 level after results are returned from the lab and the subject's participation in the study is complete.
7. Monitoring of Subjects:
  - Subjects will be encouraged to call RC at any time with study questions. RC will also call each subject weekly to ensure procedures are being followed and answer any questions. The weekly "check-in call" will occur for 12 weeks.
  - Each subject will be checking their blood pressure. Subjects will report their blood pressure via REDCap in their bi-weekly survey. Reported adverse events will be documented.

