  - Subjects in both arms will be tracked for 3 months (12 weeks). An interim analysis will be done for a sub-sample (the first 20 subjects) after three weeks of participation to determine if any arm should be adjusted or terminated.
  - Participants will continue to receive standard of care and follow up for any routine conditions being managed at HackensackUMC.
8. The final study activity will include the 2nd spot blood sample and a short survey (survey link emailed to subject via REDCap) to collect feasibility and acceptability data. The survey will take about 10 minutes to complete.

9. Subjects will then be mailed a \$40 gift card for completing the study.

10. Subjects will be informed of their omega-3 level after results are returned from the lab and the subject's participation in the study is complete

Any subject missing both daily doses 3 times a week for 3 weeks in a row will be removed from the study for non-compliance, and asked to dispose of any unused study supplement/placebo. This will be documented in a dedicated RedCap survey for anyone who discontinues study participation, either for non-compliance or of their own will.

Any subject who has another covid-19 infection during study participation may continue on the study. The RC will inform the subject of this if/when any subject reports a new covid infection.

[figure not shown]

Figure 1: Study Schema

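### The missed-dose item in the primary-endpoint survey is worded in the negative, so a subject who skipped doses may tick No and be recorded on that item as never having missed one

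*Combined protocol and SAP*

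**What the plan says.** Section 4.1 sets feasibility and acceptability as the primary endpoint and names the source: "The Follow-up Feasibility Survey (Appendix D) will be used for this analysis".

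In that survey the adherence questions run in this order:

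- A yes/no item: "Did you not take the pills (skip one or more doses) at any time during 12-week study", with the prompt "please refer to your pill log calendar". The options are printed as No, then Yes.
- A conditional item: "If yes, how often did you not take the pills".
- "For how many days in a typical week did you take the pills", printed with no condition.
- "Please include any comments about missed doses here", also printed with no condition.

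Outside the survey, Section 6.2 provides for contact during the study: "RC will also call each subject weekly to ensure procedures are being followed and answer any questions". It also has a removal rule: "Any subject missing both daily doses 3 times a week for 3 weeks in a row will be removed from the study for non-compliance". A count of remaining pills is requested only on the Study Discontinuation Verification form in Appendix D, which Section 6.2 reserves for subjects who discontinue.

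**The concern.** A negative question with a yes/no answer invites reversed replies. Someone who skipped doses can tick No in the sense of not having taken them. The layout adds to the risk, because this is the one place in the survey where No comes first.

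The two possible slips do not have the same consequence. A subject with perfect intake who ticks Yes by mistake is led to the question on how often and can put the answer right there. A subject who skipped doses and ticks No by mistake is not directed to that question.

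At stake is the reported share of subjects who never missed a dose, one of the few intake figures this survey can give a study meant to show whether a larger trial is workable.

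**Working it through.** The plan gives no expected adherence and no misreading rate, so there is no figure to reproduce. The check is a reading of the item and of the other data that could correct it, followed by an illustration with assumed inputs.

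**1. Layout.** The follow-up survey has six items with Yes and No among their options: clear instructions, missed doses, ease of taking, interference with activities, future contact and vaccination. Five list Yes first; only the missed-dose item lists No first. The other three yes/no items about the pills or their instructions also offer a neutral option; this one does not.

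**2. What could correct a mistaken No?**

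| Source | What it can show | What it can miss |
|---|---|---|
| Days per typical week (Appendix D) | Whole days regularly missed | A day with one of two doses missed; skips outside a typical week |
| Comment field (Appendix D) | Anything volunteered | Anything not volunteered |
| Weekly calls (6.2, 17.3) | Problems raised, kept as notes | No structured dose count is described |
| Removal rule (6.2, 14.0) | Sustained missing of both daily doses | Single-dose or scattered skips |
| Pill count (Appendix D) | Remaining capsules at discontinuation | Completers |
| Pill log calendar (Appendix D) | Memory aid for the subject | Nothing says it is collected |

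**3. How much the days item can miss.** Dosing is twice daily for 12 weeks, so scheduled doses = 12 × 7 × 2 = 168. A subject who misses 1% of doses misses 168 × 0.01 = 1.68 doses in 12 weeks and can truthfully answer 7 days. At the extreme, a subject who misses one of the two doses every day misses 84 of 168. That subject could still answer 7 days if any intake counts as a day, and would never miss both daily doses.

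**4. How common at least one skip may be.** Assume each dose is taken independently with probability p. Then the share with no skip is p^168:

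- p = 0.98: 3.4%
- p = 0.99: 18.5%
- p = 0.995: 43.1%

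So even with very good adherence, many subjects would have at least one skip to report.

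**5. Illustration.** Let s be the true share of subjects who skipped at least one dose, and m the share of those who misread the item and tick No. Neither value is in the documents. Assume that mistaken Yes answers are corrected at the question on how often. Then the falsely recorded share is s × m, and the recorded never-missed share is (1 − s) + s × m. Per 100 subjects:

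| s | True never missed | Recorded never missed, m = 5% / 10% / 20% | Falsely recorded, m = 5% / 10% / 20% |
|---|---|---|---|
| 40% | 60 | 62 / 64 / 68 | 2 / 4 / 8 |
| 60% | 40 | 43 / 46 / 52 | 3 / 6 / 12 |
| 80% | 20 | 24 / 28 / 36 | 4 / 8 / 16 |

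At s = 80% and m = 10%, the recorded share with a missed dose is 0.8 × 0.9 = 72%. If mistaken Yes answers are equally frequent and stay uncorrected, it is 0.8 × 0.9 + 0.2 × 0.1 = 74%. In both cases 8 of 100 subjects are falsely recorded as never having missed a dose.

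**The case against.** The best defence is that the item explains itself. The parenthesis says that skipping one or more doses is what is meant, and the next line treats Yes as having skipped. A reader might infer that No has two equally good meanings. The text does not support that: it has one intended meaning and a risk of misreading it. This part of the defence stands.

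It is also fair to say that the follow-up as a whole is not lost. Only the question on how often is conditional as printed. The days-per-week item is positively worded and open to everyone, and it can contradict a mistaken No where non-adherence is more than occasional. The appendix shows no REDCap branching, so even the conditional line may be visible to all and prompt a correction. One therefore cannot conclude that a non-adherent subject would pass through the survey as fully adherent.

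Finally, the plan sets no adherence threshold and does not say that this item classifies anyone. If most subjects miss at least one of 168 doses, a yes/no answer carries limited information anyway. That reduces the weight of the point. It does not remove it, because scattered and single-dose skips are what this item is there to catch, and the other sources in the plan may not recover them.

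**Conclusion.** The point stands as a minor, avoidable measurement weakness in the instrument for the primary endpoint. It concerns this one item. A mistaken No overstates the share who never missed a dose, and for scattered or single-dose skips nothing else specified for completers reliably corrects it.

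The size is unknown. The illustrative 2 to 16 of 100 subjects rests wholly on the assumed skip and misreading rates and gives no credit to the days-per-week or comment items. It shows direction and possible scale only. It would be wrong to infer that the primary endpoint is biased by a known amount, since the plan does not say how this item enters the feasibility assessment. No sample size, significance level or treatment comparison depends on it.

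**What to change.** Replace the item with a positive one: *Did you miss one or more doses at any time during the 12 weeks? Yes / No*, with Yes first as elsewhere in the survey. Keep the pointer to the pill log. Then ask every subject how many doses were missed, with 0 allowed, so that the two answers check each other. Add a line saying how a conflict between them will be resolved. The existing days-per-week and comment items can stay as they are.

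The cost is one edited survey item, a follow-up question shown to all, and a slightly longer response for subjects who missed no doses. Section 20.1 puts the surveys under IRB approval, so the edit would go through that route.
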